6.1 Information to be collected on screening failures

All subjects who have signed an informed consent but who cannot or chose not to enter the CAIN457A2304E1 treatment period will be considered screen failures. If the subject discontinues before enrollment, the IRT must be called within two days and the reason for not being enrolled will be entered on the Screening Phase Disposition electronic Case Report Form (eCRF). The Screening visit date, Informed Consent eCRF, Inclusion/Exclusion Criteria eCRF must be completed. If the subject has any SAE in the screening period (between signing the ICF and being enrolled), the Adverse Event eCRF and a paper SAE form must be completed.

If a subject fails to be treated in the extension study, the subject completes the follow-up visits in the respective core study.

The Withdrawal of consent eCRF should be completed if consent was withdrawn during the screening period before the subject was enrolled. The Death eCRF should be completed in the case of a death during the screening period.

6.2 Patient demographics/other baseline characteristics

The following information will be based on information derived from core study CAIN457A2304 or CAIN457A2307. This information will not be reentered into the CAIN457A2304E1 eCRFs.

Subject demographic and baseline characteristic data to be collected on all subjects include: date of birth, age, sex, race, ethnicity, source of subject referral, and on-going concomitant medications (relative to core studies) present before signing informed consent for this extension study.

6.3 Treatment exposure and compliance

All doses of study treatment administration will be recorded on the appropriate Dosage Administration Record eCRF page.

Compliance will be assessed by Novartis study personnel at each visit using vials counts and information provided by the pharmacist or the qualified site personnel.

6.4 Efficacy

All efficacy assessments should be performed prior to administration of study treatment.

It is important to **perform the IGA before the PASI**, as the knowledge of PASI scoring can potentially influence how the evaluator scores the IGA. Therefore, the following order should be applied when performing the efficacy assessments during study visits:

- Investigator's Global Assessment (IGA mod 2011; scale from 0 – 4)
- Psoriasis Area and Severity Index (PASI; score from 0 – 72)
- Rebound assessment

6.4.1 Investigator's global assessment (IGA mod 2011)

IGA mod 2011 will be conducted for overall psoriatic disease as indicated in [Table 6-1](#). It is recommended that the same evaluator conducts the assessment throughout the study whenever possible.

The IGA mod 2011 rating scale for overall psoriatic disease is shown in [Table 6-2 The IGA mod 2011 rating scale](#).

The IGA mod 2011 scale has been used in the core studies CAIN457A2304 and CAIN457A2307, and is a modified version of the scale used in secukinumab phase II studies; it was developed in collaboration with health authorities.

The IGA mod 2011 used in this study is static, i.e. it refers exclusively to the subject's disease state at the time of the assessments, and does not attempt a comparison with any of the subject's previous disease states, whether at baseline or at a previous visit.

The IGA mod 2011 score will be recorded in the eCRF.

Table 6-2 The IGA mod 2011 rating scale

Score	Short description	Detailed description
0	Clear	No signs of psoriasis. Post-inflammatory hyperpigmentation may be present.
1	Almost clear	Normal to pink coloration of lesions; no thickening; no to minimal focal scaling
2	Mild	Pink to light red coloration; just detectable to mild thickening; predominantly fine scaling
3	Moderate	Dull bright red, clearly distinguishable erythema; clearly distinguishable to moderate thickening; moderate scaling
4	Severe	Bright to deep dark red coloration; severe thickening with hard edges; severe / coarse scaling covering almost all or all lesions

Note: Involvement of nails is not part of the assessment.

Based on this scale, a subject will be considered as IGA 0 or 1 responder if the subject achieves a score of 0 or 1 and improved by at least two points on the IGA scale compared to baseline.

6.4.2 Assessment of the psoriasis area and severity index (PASI)

The investigator or qualified designee will complete the PASI assessment as indicated in [Table 6-1](#). Whenever possible, the same evaluator should perform this assessment at all visits.

A PASI score ([Fredriksson and Pettersson 1978](#), [Weisman et al 2003](#), [Gottlieb et al 2005](#)) will be derived as indicated in [Table 6-3](#). The head, trunk, upper limbs and lower limbs are assessed separately for erythema, thickening (plaque elevation, induration), and scaling (desquamation). The average degree of severity of each sign in each of the four body regions is assigned a score of 0-4. The area covered by lesions on each body region is estimated as a percentage of the total area of that particular body region. Further practical details help the assessment:

1. The neck is assessed as part of the head.

2. The axillae and groin are assessed as part of the trunk.
3. The buttocks are assessed as part of the lower limbs.
4. When scoring the severity of erythema, scales should not be removed.

Table 6-3 The PASI scoring system

Body region	Erythema (E)	Thickening (plaque elevation, induration, I)	Scaling (desquamation) (D)	Area score (based on true area %, A)*
Head (H)**	0=none	0=none	0=none	0 = 0%
	1=slight	1=slight	1=slight	1 = 1-9%
	2=moderate	2=moderate	2=moderate	2 = 10-29%
	3=severe	3=severe	3=severe	3 = 30-49%
	4=very severe	4=very severe	4=very severe	4 = 50-69%
				5 = 70-89%
				6 = 90-100%
Trunk (T)***	0=none	0=none	0=none	0 = 0%
	1=slight	1=slight	1=slight	1 = 1-9%
	2=moderate	2=moderate	2=moderate	2 = 10-29%
	3=severe	3=severe	3=severe	3 = 30-49%
	4=very severe	4=very severe	4=very severe	4 = 50-69%
				5 = 70-89%
				6 = 90-100%
Upper limbs (U)	0=none	0=none	0=none	0 = 0%
	1=slight	1=slight	1=slight	1 = 1-9%
	2=moderate	2=moderate	2=moderate	2 = 10-29%
	3=severe	3=severe	3=severe	3 = 30-49%
	4=very severe	4=very severe	4=very severe	4 = 50-69%
				5 = 70-89%
				6 = 90-100%
Lower limbs (L) ****	0=none	0=none	0=none	0 = 0%
	1=slight	1=slight	1=slight	1 = 1-9%
	2=moderate	2=moderate	2=moderate	2 = 10-29%
	3=severe	3=severe	3=severe	3 = 30-49%
	4=very severe	4=very severe	4=very severe	4 = 50-69%
				5 = 70-89%
				6 = 90-100%

* Percentage (not score) of body region (not whole body) affected will be entered in the eCRF

**Neck is assessed as part of the Head (H) body region.

***Axillae and groin are assessed as part of the Trunk (T) body region.

****Buttocks are assessed as part of the Lower limbs (L) body region.

Because the head and neck, upper limbs, trunk and lower limbs correspond to approximately 10%, 20%, 30% and 40% of the body surface area, respectively, the PASI score is calculated using the formula:

$$\text{PASI} = 0.1(\text{EH}+\text{IH}+\text{DH})\text{AH} + 0.2(\text{EU}+\text{IU}+\text{DU})\text{AU} + 0.3(\text{ET}+\text{IT}+\text{DT})\text{AT} + 0.4(\text{EL}+\text{IL}+\text{DL})\text{AL}$$

The keys for the letters are provided in [Table 6-3](#).

PASI scores can range from a lower value of 0, corresponding to no signs of psoriasis, up to a theoretic maximum of 72.0.

The **investigator** is only responsible for collecting the **components** or scoring signs and total regional area. PASI calculations, including changes over time will be done by Novartis via the PASI Score eCRF. At Week 52 and every visit throughout the extension study, the investigator or qualified designee should ensure that all the information required for the PASI calculation was entered into the PASI Score eCRF and that a PASI score is available prior to contacting IRT. The start of relapse status will be automatically calculated in the PASI score eCRF for the specific visit. Based on the start of relapse status, IRT will assign a medication number. This will be transmitted to the pharmacist for the preparation of the appropriate study treatment to be administered to the subject.

Definitions of efficacy variables based on PASI

The following definitions are used in this study (see CHMP guidelines for psoriasis ([CHMP/EWP/2454/02 2004](#))), baseline referring to randomization visit in CAIN457A2304:

- **PASI 50 response:** subjects achieving $\geq 50\%$ improvement (reduction) in PASI score compared to baseline are defined as PASI 50 responders
- **PASI 75 response:** subjects achieving $\geq 75\%$ improvement (reduction) in PASI score compared to baseline are defined as PASI 75 responders
- **PASI 90 response:** subjects achieving $\geq 90\%$ improvement (reduction) in PASI score compared to baseline are defined as PASI 90 responders
- **PASI 100 response/remission:** complete clearing of psoriasis (PASI=0)
- **Relapse:** when the achieved maximal PASI improvement from baseline is reduced by $>50\%$
- In addition to the above, the following definition is also used in this protocol:
- **Start of relapse:** loss of $\geq 20\%$ of the maximum PASI gain in CAIN457A2304 or CAIN457A2304E1 (compared to baseline of the core study) achieved at any time before the visit at which the assessment is made and loss of PASI 75 response
- **PASI Partial response:** Subjects achieving at least 50%, but less than 75% reduction of PASI compared to baseline (i.e PASI 50 but not a PASI 75 response)
- **PASI Non response:** Subjects achieving less than 50% reduction of PASI compared to baseline

6.4.2.1 Assessment of rebound

Rebound of disease will be assessed as indicated in [Table 6-1](#).

In addition, to the assessment of PASI, the investigator will assess whether new pustular psoriasis, or new erythrodermic psoriasis, or more inflammatory psoriasis occurred (yes/no).

6.4.3 Appropriateness of efficacy assessments

PASI scores outcome measures, the assessment of the severity of the psoriasis symptoms and the extent to which the subject's body area is affected by the disease, is mandated by the EMA for psoriasis (CHMP guideline on the treatment of psoriasis-[CHMP/EWP/2454/02 2004](#)).

6.5 Safety

All blood draws and safety assessments should be done prior to study treatment administration. Appropriate safety assessments (e.g. evaluation of AEs and SAEs including injection site reactions) should be repeated after the dose is administered.

- Evaluation of all AEs and SAEs including injection site reactions
- Physical examination
- Vital signs
- Laboratory evaluations
- Hematology
- Clinical chemistry
- Urinalysis
- Immunogenicity (assessment of anti-seukinumab antibody development)
- Electrocardiogram
- Pregnancy and assessments of fertility

For frequency of assessments, see [Table 6-1](#)

6.5.1 Physical examination

A physical examination, including general appearance, skin, neck, eyes, ears, nose, throat, lungs, heart, abdomen, back, lymph nodes, extremities, vascular and neurological systems will be performed as indicated in [Table 6-1](#).

If possible, assessments for an individual subject should be performed by the same member of the study site staff throughout the study.

Information for all physical examinations must be included in the source documentation at the study site. Significant findings that are present prior to the signing of the informed consent form will have been already entered during core study in the Medical History screen on the subject's eCRF. Significant findings made after signing informed consent which meet the definition of an Adverse Event must be recorded on the Adverse Event screen of the subject's eCRF ([Section 7](#)).

6.5.2 Vital signs

Vital signs (including blood pressure and pulse measurements) will be assessed at every scheduled visit as indicated in [Table 6-1](#).

After the subject has been sitting for five minutes, with back supported and both feet placed on the floor, systolic and diastolic blood pressure will be measured twice (measurements separated by 1 to 2 minutes) using a validated device, with an appropriately sized cuff. In case the cuff sizes available are not large enough for the subject's arm circumference, a sphygmomanometer with an appropriately sized cuff may be used ([Mancia et al 2007](#)). On the Vital Signs eCRF, the average of the two measurements will be entered. If possible, assessments should be performed by the same study site staff member throughout the study.

Normal blood pressure will be defined as a systolic pressure of 90 to <120 mmHg, and a diastolic blood pressure of 60 to <80 mmHg under the measurement conditions outlined above. Notable blood pressure will be hypertension (systolic \geq 140 mmHg and/or diastolic \geq 90 mmHg) or hypotension (systolic <90 mmHg and/or diastolic <60 mmHg). A blood pressure indicative of prehypertension (systolic 120 to < 140 mmHg and/or diastolic 80 to < 90 mmHg) will not be regarded as notable ([Chobanian et al 2003](#)). A normal pulse rate will be defined as a rate of 60 to 100 beats per minute under the measurement conditions outlined above. Notable pulse rates are a rate below 60 bpm (bradycardia) or above 100 bpm (tachycardia).

The investigator will decide whether action needs to be taken to address notable vital signs, taking into account the overall status of the subject. No specific action is foreseen as part of the study protocol.

6.5.3 Height and weight

Height and weight will be based on information derived from core study CAIN457A2304 or CAIN457A2307. This information will not be reentered into the CAIN457A2304E1 eCRFs at Week 52 (enrollment) and body weight will be measured as listed in [Table 6-1](#). Body weight will be measured in indoor clothing, but without shoes. If possible, body weight assessments should be performed by the same study site staff member and using the same scale throughout the study.

6.5.4 Laboratory evaluations

Subjects should avoid smoking within the hour preceding the blood draws. A central laboratory will be used for analysis of all specimens listed below, unless noted otherwise. Details on the collections, shipment of samples and reporting of results by the central laboratory are provided to investigators in the laboratory manual. Refer the Laboratory Manual for identification of laboratory reference range values and the schema for notification of site staff and Novartis for out of range values.

[Appendix 1](#) shows the extended laboratory ranges that are considered clinically notable.

Whether action needs to be taken to address notable laboratory values will be decided by the investigator, taking into account the overall status of the subject. No specific action is foreseen as part of the study protocol.

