7.3 Liver safety monitoring

To ensure patient safety and enhance reliability in determining the hepatotoxic potential of an investigational drug, a standardized process for identification, monitoring and evaluation of liver events has to be followed.

Liver events are divided into two categories:

- Liver events of special interest (AESI) which consist of LFTs elevations
- Medically significant liver events which are considered as serious adverse events (SAEs) and which consist of marked elevations of LFTs and / or pre-specified adverse events.

Please refer to [Table 14-1](#) in [Appendix 2](#) for complete definitions of liver events.

Any liver event which meets the criteria for “medically significant” event as outlined in [Table 14-1](#) of [Appendix 2](#) should follow the **standard procedures for SAE reporting** as described in [Section 7.2](#).

Every liver event as defined in [Table 14-1](#) of [Appendix 2](#) should be followed up by the investigator or designated personal at the trial site as summarized below. Detailed information is outlined in [Table 14-2](#) in [Appendix 2](#).

- Repeating the LFT to confirm elevation as appropriate
- Discontinuation of the investigational drug if appropriate
- Hospitalization of the patient if appropriate
- A causality assessment of the liver event via exclusion of alternative causes (e.g., disease, co-medications)
- An investigation of the liver event which needs to be followed until resolution.

These investigations can include serology tests, imaging and pathology assessments, hepatologist's consultancy, based on investigator's discretion. All follow-up information, and the procedures performed should be recorded on appropriate CRF pages, including the liver event overview CRF pages.

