Newcombe RG (1998) Two-sided confidence intervals for the single proportion: comparison of seven methods. *Statistics in Medicine*; 17: 857-872.

WHO regional office for Europe, Nutrition Unit. (1988) Classification and description of anthropometric data. EUR/ICP/NUT/125 document. Copenhagen, Denmark.

13 Appendix 1: Clinically notable laboratory values and vital signs

The following criteria will be used to define expanded limits and notable abnormalities of key laboratory tests. Notable values for blood pressure and pulse are presented in [Section 6.5.2](#). Whether action needs to be taken to address notable laboratory or vital signs values will be decided by the investigator, taking into account the overall status of the subject. No specification is foreseen as part of the study protocol.

Liver Function and Related Variables

Alanine transaminase (ALT) (SGPT):	> 3 x Upper Limit of Normal (ULN)
Aspartate transaminase (AST) (SGOT):	> 3 x ULN
Total bilirubin:	> 2 x ULN
Alkaline phosphatase:	> 2.5 x ULN

Renal Function and Electrolyte Variables

Creatinine (serum):	> 1.5 x ULN
Potassium:	> 6 mmol/L or < 3 mmol/L
Sodium:	> 160 mmol/L or < 115 mmol/L

Hematology Variables

Hemoglobin:	≥ 20 g/dL decrease from baseline
Platelet count:	< Lower Limit of Normal (LLN)
White blood cell count:	< 0.8 x LLN
Neutrophils:	< 0.9 x LLN
Eosinophils:	> 1.1 x ULN
Lymphocytes:	> 1.1 x ULN

Urinalysis Variable

Protein urine dipstick:	++*
-------------------------	-----

* ++ is ≥ 100 mg/dL

14 Appendix 2: Liver event definitions and follow-up requirements

Table 14-1 Liver Event Definitions

	Definition/ threshold
Adverse event of special interest	
Laboratory values	ALT or AST > 3 x ULN ALP > 2 x ULN TBL > 1.5 x ULN
Medically significant event (SAE)	
Laboratory values	ALT or AST > 5 x ULN (with or without TBL > 2 x ULN [mainly conjugated fraction]) ALP > 5 x ULN (with or without TBL > 2 x ULN [mainly conjugated fraction]) TBL > 3 x ULN Potential Hy's Law cases (defined as ALT/AST > 3 x ULN and TBL > 2 x ULN [mainly conjugated fraction] without notable increase in ALP to > 2 x ULN)

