Adverse events	Any clinical event of jaundice (or equivalent term) ALT or AST > 3 x ULN accompanied by general malaise, fatigue, abdominal pain, nausea, or vomiting, or rash with eosinophilia Any event that links to a preferred term (PT) in the MedDRA dictionary falling under the SMQ sub-module "Drug-related hepatic disorders – severe events only" or any "Hy's law case" PT

* These events cover the following: hepatic failure, fibrosis and cirrhosis, and other liver damage-related conditions; the non-infectious hepatitis; the benign, malignant and unspecified liver neoplasms

Table 14-2 Liver Event Follow Up Requirements

Criteria	Event type	Actions required	Follow-up monitoring
Potential Hy's Law case ^a	Medically significant	Discontinue the study drug immediately Hospitalize, if clinically appropriate Report to Novartis as an SAE Establish causality	ALT, AST, TBL, Alb, PT, ALP and γGT until resolution ^c (frequency at investigator discretion)
ALT or AST			
> 8 x ULN	Medically significant	Repeat LFT within 48 hours If elevation persists, discontinue the study drug immediately Hospitalize if clinically appropriate Report to Novartis as an SAE Establish causality	ALT, AST, TBL, Alb, PT, ALP and γGT until resolution ^c (frequency at investigator discretion)
> 5 to ≤ 8 x ULN	Medically significant	Repeat LFT within 48 hours If elevation persists for more than 2 weeks , discontinue the study drug Report to Novartis as an SAE Establish causality	ALT, AST, TBL, Alb, PT, ALP and γGT until resolution ^c (frequency at investigator discretion)
> 3 x ULN accompanied by symptoms ^b	Medically significant	Discontinue the study drug immediately Hospitalize if clinically appropriate Report to Novartis as an SAE Establish causality	ALT, AST, TBL, Alb, PT, ALP and γGT until resolution ^c (frequency at investigator discretion)
> 3 to ≤ 5 x ULN (patient is asymptomatic)	AESI	Central laboratory to report to Investigator & Novartis Repeat LFT once or twice in the week If elevation persists, establish causality	Investigator discretion Monitor LFT within 1 to 4 weeks or at next visit
≤ 3 x ULN (patient is asymptomatic)	N/A	Repeat LFT at next visit	
ALP (isolated)			
> 5 x ULN	Medically significant	Repeat LFT within 48 hours If elevation persists, report to Novartis as an SAE Establish causality	Investigator discretion Monitor LFT within 1 to 4 weeks or at next visit

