> 2 to ≤ 5 x ULN (patient is asymptomatic)	AESI	Central laboratory to report to Investigator & Novartis	Investigator discretion Monitor LFT within 1 to 4 weeks or at next visit

Criteria	Event type	Actions required	Follow-up monitoring
		Repeat LFT once or twice in the weekIf elevation persists, establish causality	
≤ 2 x ULN (patient is asymptomatic)	N/A	Repeat LFT at next visit	
TBL (isolated)			
> 3 x ULN	Medically significant	Repeat LFT within 48 hours If elevation persists, discontinue the study drug immediately Hospitalize if clinically appropriate Report to Novartis as an SAE Establish causality	ALT, AST, TBL, Alb, PT, ALP and γGT until resolution ^c (frequency at investigator discretion) Test for hemolysis (e.g., reticulocytes, haptoglobin, unconjugated [indirect] bilirubin)
> 1.5 to ≤ 3 x ULN (patient is asymptomatic)	AESI	Central laboratory to report to Novartis Repeat LFT once or twice in the weekIf elevation persists, establish causality	investigator discretion Monitor LFT within 1 to 4 weeks or at next visit
≤ 1.5 x ULN (patient is asymptomatic)	N/A	Repeat LFT at next visit	
Preferred terms			
Jaundice	Medically significant	Discontinue the study drug immediately Hospitalize the patient Report to Novartis as an SAE Establish causality	ALT, AST, TBL, Alb, PT, ALP and γGT until resolution ^c (frequency at investigator discretion)
“Drug-related hepatic disorders - severe events only” SMQ AE	Medically significant	Discontinue the study drug hospitalization if clinically appropriate Report to Novartis as an SAE Establish causality	Investigator discretion

^a Elevated ALT/AST > 3 x ULN and TBL > 2 x ULN but with no notable increase in ALP to > 2 x ULN

^b General malaise, fatigue, abdominal pain, nausea, or vomiting, rash with eosinophilia

^c Resolution is defined as an outcome of one of the following: return to baseline values, stable values at three subsequent monitoring visits at least 2 weeks apart, remain at elevated level after a maximum of 6 months, liver transplantation, and death.

15 Appendix 3: Blood collection log for pharmacokinetics (PK) and immunogenicity (IG)

Table 15-1 Blood collection log for PK

Visit Name	Time point	Volume (approx .)	Analyte	Sample number	Dose Reference ID/ PK collection number**
Week 52 ¹	Pre-dose	(2 mL)	AIN457 for PK	(5)	(5)
Week 64	Pre-dose	2 mL	AIN457 for PK	7	7
Week 76	Pre-dose	2 mL	AIN457 for PK	8	8
Week 104	Pre-dose	2 mL	AIN457 for PK	9	9
Week 116	Pre-dose	2 mL	AIN457 for PK	10	10

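### Isolated ALP above 5 x ULN has two inconsistent SAE rules; separately, Section 6.5.4 and Appendix 1 leave action on notable laboratory values to the investigator without exempting liver tests

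*Protocol*

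**What the plan says.** **Isolated ALP above 5 x ULN.** Protocol Table 14-1 (Appendix 2) lists ALP above 5 x ULN, whether or not bilirubin is raised, as a medically significant event and labels that class SAE. It attaches no persistence condition. Section 7.3 sends medically significant liver events to standard SAE reporting, and Section 7.2 sets 24 hours from awareness. In Table 14-2, the row for isolated ALP above 5 x ULN asks for a repeat liver function test (LFT) within 48 hours and an SAE report if the elevation persists.

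**Notable laboratory values in general.** Section 6.5.4 refers to Appendix 1 for the notable ranges and continues: "Whether action needs to be taken to address notable laboratory values will be decided by the investigator". It adds: "No specific action is foreseen as part of the study protocol". Appendix 1 says much the same: "Whether action needs to be taken to address notable laboratory or vital signs values will be decided by the investigator". Neither place exempts liver tests or points to Section 7.3 or Appendix 2.

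**The liver procedure.** Section 7.3 states that "a standardized process for identification, monitoring and evaluation of liver events has to be followed". Table 14-2 has a column headed "Actions required". For asymptomatic ALT or AST above 3 and up to 5 x ULN it includes "Repeat LFT once or twice in the week". For a potential Hy's Law case, or ALT or AST above 3 x ULN with symptoms, it says "Discontinue the study drug immediately". For isolated bilirubin above 3 x ULN it says "If elevation persists, discontinue the study drug immediately". Section 7.3 itself qualifies the repeat test, discontinuation and hospitalization as steps to take where appropriate.

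**The concern.** Section 7.3 cannot settle the ALP question, because it relies on both tables: Table 14-1 for what counts as a medically significant event and Table 14-2 for what to do about it. Two sites with the same laboratory value can therefore each follow the protocol and reach different answers on whether it is an SAE.

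Long-term safety is the primary objective, and 675 subjects were enrolled at 112 sites. SAP Section 1.9.1 summarises SAEs separately and gives exposure-adjusted SAE rates by system organ class and preferred term, so those tables depend on how a site classified the event.

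The Section 6.5.4 issue is smaller. Someone who stops there, or at Appendix 1 (which Section 7.1 cites for alert ranges), is told that the protocol foresees no action on values for which Table 14-2 requires some.

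**Working it through.** The plan states no figure to reproduce. The check sets the texts side by side.

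**1. The two ALP rules.** Inputs: Table 14-1, Sections 7.3 and 7.2 (24 hours); Table 14-2 (repeat within 48 hours, SAE report on persistence).

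| Result of repeat test | Table 14-1 with 7.3 and 7.2 | Table 14-2 row |
|---|---|---|
| Elevation not confirmed | SAE on the first value | No SAE report called for |
| Elevation confirmed | SAE, clock starts at the first value | SAE, clock starts at the repeat value |

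**2. Timing when the elevation is confirmed.** Let t be the hours from the first result to the repeat result, with t between 0 and 48.

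- Table 14-1 route: report due at 24 hours.
- Table 14-2 route: report due at t + 24, that is 0 + 24 = 24 to 48 + 24 = 72 hours.
- Difference: 0 to 48 hours.

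This assumes that the 48 hours run from the first result and the 24 hours from the repeat result. Laboratory turnaround is not given and is left out.

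**3. Comparison with the other rows.** Table 14-2 has eight medically significant rows: potential Hy's Law; ALT/AST above 8; ALT/AST above 5 to 8; ALT/AST above 3 with symptoms; isolated ALP above 5; isolated bilirubin above 3; jaundice; and severe drug-related hepatic disorders. As the text reads, seven give the SAE report as its own instruction. In the ALT/AST above 8, ALT/AST above 5 to 8 and bilirubin above 3 rows, persistence attaches to stopping drug. Only the ALP row attaches it to the SAE report.

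**4. Section 6.5.4 against Table 14-2.** Appendix 1 lists 4 liver + 3 renal and electrolyte + 6 hematology + 1 urine = 14 parameters. Table 14-2 sets actions for the four liver tests and none for the other 14 - 4 = 10.

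| Test | Appendix 1 notable limit (x ULN) | Table 14-2 action starts above (x ULN) |
|---|---|---|
| ALT | 3 | 3 |
| AST | 3 | 3 |
| Total bilirubin | 2 | 1.5 |
| ALP | 2.5 | 2 |

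For each test the action range starts at or below the notable limit, so all four have notable values for which Table 14-2 sets actions. One limit applies: the lower ALP row (above 2 to 5) and lower bilirubin row (above 1.5 to 3) cover only isolated elevations in asymptomatic patients. A symptomatic isolated ALP above 2.5 to 5, or bilirubin above 2 to 3, has no row of its own, although Section 7.3 still requires follow-up of every liver event defined in Table 14-1.

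**The case against.** The strongest reply on ALP is that the rules are not mutually exclusive. Table 14-2 does not say that an SAE report is due solely on persistence, and nothing in it forbids earlier reporting. A site that reports within 24 hours of the first value and repeats the test within 48 hours complies with both. This stands. A reader might infer that the two rules cannot both be followed; the documents do not support that. What remains is that Table 14-2 can fairly be read as excusing the report when the repeat is normal.

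A second reply concerns layout. The line structure of Table 14-2 is partly lost in the text available here, so the SAE line in the ALT/AST above 8, ALT/AST above 5 to 8 and bilirubin rows might have been nested under persistence. The seven-of-eight count is therefore the natural reading, not a certainty. The mismatch with Table 14-1 does not depend on it.

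On Section 6.5.4, a reader might infer that the protocol has no binding liver rule or leaves liver safety to discretion. It does not: Section 7.3 makes the process mandatory, and Appendix 2 directly follows Appendix 1. Section 6.5.4 also refers to a notification scheme in the Laboratory Manual, which was not available. The where-appropriate qualifiers in Section 7.3 narrow the contrast further, but they do not remove the SAE reporting and causality steps.

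Finally, it is tempting to say that no SAP analysis is affected. That holds for the counts in SAP Table 1-19, which use laboratory values, but not for the SAE tables and rates.

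**Conclusion.** The ALP inconsistency is real and worth fixing. It can change whether an unconfirmed isolated ALP above 5 x ULN is recorded as an SAE. For a confirmed one it can move the reporting deadline from 24 hours to anywhere between 24 and 72 hours, on the timing assumptions above. The likely effect on SAE summaries and incidence rates is small, since it concerns one laboratory criterion. The documents give no count of affected subjects, so it cannot be sized further.

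The Section 6.5.4 and Appendix 1 wording is a secondary cross-reference defect. It is wrong for the liver values that Table 14-2 covers, but Section 7.3 governs, so the risk is confined to someone who reads no further. Confidence in both textual conflicts is high.

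**What to change.** **ALP.** In the Table 14-2 row for isolated ALP above 5 x ULN, remove the persistence condition from SAE reporting and keep the 48-hour repeat as follow-up. This matches Table 14-1, Section 7.3 and the 24-hour rule in Section 7.2. The cost is a few more SAE reports for elevations that the repeat does not confirm. If the sponsor's safety physicians prefer confirmation first, the alternative is to add the persistence condition to Table 14-1 and Section 7.3; either way, one rule should stand.

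**Section 6.5.4 and Appendix 1.** Add to both an exception for liver events, stating that Section 7.3 and Table 14-2 apply.

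Both changes are wording for an amendment and a site letter, with no new procedures. SAP Section 1.12 records a five-year interim analysis as already done. If an amendment is no longer practical, check that all ALP values above 5 x ULN were classified by one rule and state that rule in the study report.
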